4.0 Test Schedule

	Pre-treatment/ Baseline ≤30 days prior to registration	Hypo-fractionated RT 42.75 Gy in 15 fractions	Post-RT Assessment (+/- 5 days)	Pre- Operative Assessment Within 2 weeks of surgery⁹	Post- Operative Assessment 4-8 weeks Post-Surgery^{6,9}	Years 1 & 2 Post-Surgery Assessment Every 6 Months Post-Surgery^{7,8,9} (+/- 8 weeks)	Years 3-5 Post-Surgery Assessment Annually Post- Surgery^{7,8,9} (+/- 8 weeks)
History, physical exam ⁷ , ECOG status	X		X	X		X	X
Pathology review ¹	X				X		
Primary site MRI ² , ⁵	X			X		X	X
PET/CT or CT Chest ⁵ ,	X			X		X	X
Pregnancy test ³	X						
AE Acute Assessment (See section 10.0)	X		X	X			
Hypofractionated RT		X					
CTCAE v5.0 Solicited Late Toxicity Assessment (See section 10.0)	X				X	X	X
Wound Complication Assessment (Appendix VI/Section 11.0)					X	X	
Regional Alopecia Assessment (Appendix V)	X		X	X			
Joint Stiffness Assessment (Appendix IV)	X		X	X		X	X
PROMISE-10 ^a	X			X		X ⁴	
TESS ^b	X			X		X ⁴	

1. Pathology review includes histopathologic diagnosis of soft tissue sarcoma and grade, where applicable.
2. CT is acceptable if MRI is not advisable.
3. For women of childbearing potential only. Must be done ≤7 days prior to beginning radiation treatment. Tubal ligation and IUD in place are exceptions.
4. Obtained at 12, 18, and 24 months.
5. Within 60 days of enrollment
6. Follow Up timepoints may be evaluated outside the anticipated window as deemed appropriate by Stand of Care Radiation Oncology and Orthopedic Surgery follow up schedule
 - a. Patient-Reported Outcomes Measurement Information System
 - b. Toronto Extremity Salvage Score
7. Assessments may be completed by NP/PA in person or by virtual and/or phone visit if patient is unable to return to study site.
8. Per physician discretion
9. If patient develops any type of disease progression or is unwilling to return to the institution, patients will move to yearly survival follow up. No additional assessments will need to be done.

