16.3.2 Secondary Outcome Analysis

16.3.2.1 Local failure is defined any radiographic or pathologic evidence of recurrent disease inside the CTV and/ or to within 3 cm from the edge of the CTV. In the absence of censored patients prior to 5 years, local failure rate at 5 years (LFR5) will be equal to the binomial proportion. LFR5 will be evaluated by the number of patients free of local failure/recurrence at 5 year divided by the total number of evaluable patients. Exact binomial 95%

confidence interval for the point estimate will be provided. In the case of censoring prior to 5 years, LFR5 will be estimated using the Kaplan-Meier method.

- 16.3.2.2 Disease-Free Survival is defined as the time from registration date to the earliest date of documentation of either, local recurrence, regional recurrence, distant recurrence, or death due to any cause, censoring patients who are alive and local recurrence free at the date of last known clinical assessment. The distribution of disease-free survival will be estimated using method of Kaplan-Meier.
- 16.3.2.3 Overall Survival is defined as the time from registration date to death due to any cause, censoring patients alive at the date of last contact. The distribution of overall survival will be estimated using method of Kaplan-Meier.
- 16.3.2.4 Late toxicity is defined as toxicity occurs any time between 3 months and 24 months after completion of hypofractionated preoperative radiation therapy. The rate of \geq grade 2 late toxicities will be estimated by the number of patients with a \geq grade 2 late toxicity divided by the total number of evaluable patients. Exact binomial 95% confidence intervals for the true rate of \geq grade 2 toxicity events will be calculated.
- 16.3.2.5 Pattern of relapse will be evaluated by number of patients with patterns of tumor recurrence such as local recurrence, marginal recurrence, regional recurrence, distant metastasis, and second primary tumor divided by the total number of evaluable patients. Exact binomial 95% confidence interval for the point estimate will be provided.
 - 16.3.2.5.1 Local tumor recurrence is defined as any tumor recurrence inside the CTV.
 - 16.3.2.5.2 Marginal tumor recurrence is defined as any tumor recurrence beyond the CTV to within a 3 cm distance from the edge of the CTV.
 - 16.3.2.5.3 Distant tumor recurrence is defined as any tumor that develops distantly from the primary site of sarcoma.

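### The late-toxicity rate has no rule for patients whose grading stops before 24 months, and on the natural reading it counts them as toxicity-free

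*Combined protocol and SAP*

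**What the plan says.** Objective 2.2.4 is to report long-term toxicity rates. Section 16.3.2.4 carries it out: "Late toxicity is defined as toxicity occurs any time between 3 months and 24 months after completion of hypofractionated preoperative radiation therapy". The numerator is patients with at least one event of grade 2 or higher. The rate is patients with a "grade 2 late toxicity divided by the total number of evaluable patients", with an exact binomial 95% interval. The section does not define evaluable and does not mention incomplete follow-up.

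Section 16.3.2.6 treats every eligible patient who started treatment as evaluable for adverse event rates. It tabulates maximum grades with no stated end date and refers late toxicity back to 16.3.2.4 for a separate summary.

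In the Test Schedule (4.0), solicited late toxicity is marked after surgery, every 6 months in years 1 and 2, and annually in the column headed "Years 3-5 Post-Surgery Assessment". Three footnotes bear on whether grading takes place:

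- Footnote 9: "If patient develops any type of disease progression or is unwilling to return to the institution, patients will move to yearly survival follow up". It adds: "No additional assessments will need to be done".
- Footnote 8, on both follow-up columns: "Per physician discretion".
- Footnote 7 allows virtual or telephone assessment for patients who cannot return.

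For local failure, 16.3.2.1 does have a rule: "In the case of censoring prior to 5 years, LFR5 will be estimated using the Kaplan-Meier method". Disease-free and overall survival are also estimated by Kaplan-Meier with censoring.

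**The concern.** A crude proportion with a binomial interval assumes that each patient's outcome is known over the whole window. Footnote 9 ensures that for some patients it is not. A patient who progresses at month 8 without a grade 2 event is graded no further, yet stays in the denominator as a non-event up to month 24. The protocol itself creates this missing information, and the neighbouring endpoints in the same section have a method for it.

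At stake is the long-term safety figure for a new fractionation schedule. Section 1.0 gives lower irreversible late toxicity as a main reason for preoperative radiation, so a rate that looks low because some patients were no longer examined would be misread. A second, smaller gap is that no late-toxicity estimate or interval is planned for toxicity graded in years 3 to 5.

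**Working it through.** **The plan's own figures.** The plan gives no expected rate, precision or sample size for late toxicity. Its only design figures concern wound complications. They reproduce: [(1.2816·√(0.45·0.55) + 0.8416·√(0.35·0.65)) / 0.10]² = 107.95, so 108 patients, and 108/0.90 = 120. They are not affected. The 108 is used below only to turn rates into patients.

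**Who is counted.** Setting 16.3.2.4, 16.3.2.6 and footnote 9 side by side:

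| Patient | Graded to 24 months? | Counted as |
|---|---|---|
| Grade 2+ event before grading stops | not needed | event |
| No event, graded to 24 months | yes | non-event, correctly |
| No event, dies before 24 months | to death | non-event, correct for a cumulative incidence |
| No event, progression-free, stops returning | no | non-event, outcome unknown |
| No event, progresses, grading stops | no | non-event; correct only if the target is toxicity before progression |

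The last two rows are the problem. If progression is treated as a competing event and nobody is lost for another reason, the cumulative incidence at 24 months equals events divided by patients, which is the crude proportion. Progressors then add no bias. If the target is toxicity whether or not the patient progresses, their unseen events are missing from the numerator.

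**Size, as an illustration.** Inputs:

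- p, the true 24-month rate: 31.5% or 15.1%. These are the fibrosis and edema figures after preoperative radiation in Section 1.0. Their grade and time point are not given there, and neither is the composite of any grade 2+ toxicity.
- q, the share leaving assessment alive between 3 and 24 months: 10%, 20% or 30%, assumed. The only loss figure in the documents is about 10%, for the 120-day endpoint (16.2.2).
- Leaving time and onset time are independent and uniform over 3 to 24 months, and leavers' unseen events belong to the target.

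Half of the leavers' events then come before leaving, so

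crude rate = p(1 − q) + p·q/2 = p(1 − q/2).

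| p | q | crude rate | shortfall (points) | events missed in 108 |
|---|---|---|---|---|
| 31.5% | 10% | 0.315 × 0.95 = 29.9% | 1.6 | 1.7 of 34.0 |
| 31.5% | 20% | 0.315 × 0.90 = 28.4% | 3.2 | 3.4 of 34.0 |
| 31.5% | 30% | 0.315 × 0.85 = 26.8% | 4.7 | 5.1 of 34.0 |
| 15.1% | 10% | 0.151 × 0.95 = 14.3% | 0.8 | 0.8 of 16.3 |
| 15.1% | 20% | 0.151 × 0.90 = 13.6% | 1.5 | 1.6 of 16.3 |
| 15.1% | 30% | 0.151 × 0.85 = 12.8% | 2.3 | 2.4 of 16.3 |

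A second model, with constant onset hazard over 3 to 24 months and exponential leaving from the end of radiation, gives 29.8%, 28.0% and 26.1% at p = 31.5%. The two agree to within a point.

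**Years 3 to 5.** Post-surgery late-toxicity assessments fall at 4-8 weeks, at 6, 12, 18 and 24 months, and at 3, 4 and 5 years: eight in all. The last three, 3 of 8, lie outside the window.

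**Clocks.** The window runs from the end of radiation and the visits from surgery. Section 7.2 puts surgery 3-4 weeks after radiation, or at the latest 6 weeks plus 1. An on-date 24-month visit therefore falls 3 to 7 weeks after the window closes.

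**The case against.** The strongest reply is that the plan never states the estimand. If late toxicity is meant as toxicity before progression, the crude proportion is right for progressors, and only progression-free patients who stop returning cause bias. That stands. A reader might infer that the rate is too low whenever anyone leaves assessment alive; the documents do not support this without a stated target.

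The denominator is also inferred. Section 16.3.2.4 does not define evaluable, and the reading used here borrows 16.3.2.6. It is the most natural reading because 16.3.2.6 covers adverse event rates and refers to 16.3.2.4, but a narrower set may have been meant.

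The number of leavers may be small. Footnote 7 permits remote visits, and criterion 3.1.9 requires willingness to return. Both bear on the assumed 10-30%. Neither helps after progression, when footnote 9 ends grading.

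Sampling error is larger than the shift: the exact 95% interval for 34 of 108 is 22.9% to 41.1%. That is true, but the shift is systematic and the interval does not cover it.

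Three further stronger readings are tempting:

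- That year 3-5 toxicity enters no rate at all. The 16.3.2.6 tables have no end date, so it may appear there; what is missing is a late-toxicity rate or interval.
- That a 24-month limit contradicts objective 2.2.4. It is a legitimate horizon and matches the patient-reported outcomes, which are analysed to 24 months.
- That the clock mismatch discards the 24-month visit. The definition speaks of when toxicity occurs, and the example worksheet in 10.3.1 records the event date, so the visit can still pick up earlier onsets. The worksheet is only an example, so dating is not fully settled, but the point is minor.

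**Conclusion.** The concern holds for the missing rule. The only planned late-toxicity rate is a crude proportion with a binomial interval, under a protocol that ends grading early for some living patients. On the natural reading of evaluable, those without an event count as toxicity-free to 24 months. This understates the rate for progression-free patients who stop returning, and for progressors too unless the target is toxicity before progression.

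Under the assumptions shown, the shortfall is about 1.6 to 4.7 points at a true rate of 31.5% and 0.8 to 2.3 points at 15.1%. The size rests on assumed leaving shares and borrowed rates, and on leaving being independent of toxicity. The downward direction rests on the denominator and the target just described.

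The absence of a late-toxicity estimate beyond 24 months is a lesser point. The endpoint is secondary and descriptive; the primary endpoint, sample size and decision rule are untouched. The change should be made, but nothing else in the trial depends on it.

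**What to change.** In 16.3.2.4:

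1. State the estimand (late toxicity regardless of progression, or before it) and define the evaluable set.
2. Add the cumulative incidence of first grade 2+ late toxicity at 24 months, with death as a competing event and censoring at the last toxicity assessment.
3. Add a sensitivity analysis with progression as a competing event, because stopping at progression may not be independent of toxicity.
4. Report the number of patients assessed at each visit.

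Optionally, report a supplementary 5-year estimate from the year 3-5 assessments already scheduled, with a caution that these visits are discretionary and ascertainment may be selective. Also optionally, state whether a toxicity is dated by onset or by the visit at which it is found.

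The cost is SAP wording and one more table. The core change uses assessments already scheduled. The reported rate may be higher than the crude proportion.

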Appendix V Regional Alopecia Assessment.....	73
Appendix VI Surgical Wound Complication Asessment.....	7

Study Schema

Localized, resectable soft tissue sarcoma of the extremity/limb girdle or superficial trunk

Pre-operative radiation therapy

Dose: 42.75 Gy in 15 fractions

Definitive surgical resection

(3-6 weeks interval between radiation therapy and definitive surgery)

Event Monitoring

List of Abbreviations

AE	Adverse Event/Adverse Experience
BID	Twice daily
cGy	centiGray
CRF	Case Report Form
CT	Computed Tomography
CTCAE	Common Terminology Criteria for Adverse Events
CTV	Clinical Target Volume
DSMB	Data and Safety Monitoring Board
DVH	Dose Volume Histogram
ECOG	Eastern Cooperative Oncology Group
eCRF	Electronic Case Report Form
ER / ES	Electronic Record and Electronic Signature
Gy	Gray
GTV	Gross Tumor Volume
ICRU	International Commission on Radiation Units and Measurements
IMPT	Intensity Modulated Proton Therapy
IMRT	Intensity Modulated Radiotherapy
IND / IDE	Investigational Drugs and Devices
IRB	Institutional Review Board
ITV	Internal Target Volume
LFR5	Local Failure Rate at 5 years
MCCC	Mayo Clinic Cancer Center
MRI	Magnetic Resonance Imaging
PROMISE	Patient-Reported Outcomes Measurement Information System
PS	Performance Status
PTV	Planning Target Volume
RBE	Relative Biological Effectiveness
RT	Radiation Therapy
SOC	System Organ Class
TESS	Toronto Extremity Salvage Score
UPIRTSO	Unanticipated Problems Involving Risks To Subjects or Others
VMAT	Volumetric Modulated Arc Therapy
3DCRT	3D Conformal Radiation Therapy

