7.2 Surgery

Patients will undergo oncologic resection ideally 3-4 weeks after completion of preoperative radiation therapy per institutional standards. If surgery is not feasible during this ideal period, it must be performed within 6 weeks (\pm 1 week) of completing preoperative radiation therapy. Acute wound complications will be recorded as detailed in section 11.1.

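### Late toxicity is counted to 24 months after radiation but assessed at visits timed from surgery, so a 24-month visit held on its due date falls 3-7 weeks outside the window

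*Combined protocol and SAP*

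**What the plan says.** Section 16.3.2.4 fixes the window from the end of radiation: "Late toxicity is defined as toxicity occurs any time between 3 months and 24 months after completion of hypofractionated preoperative radiation therapy". The rate is a simple proportion: patients with a grade 2 or higher late toxicity over evaluable patients, with an exact binomial 95% interval. Section 16.3.2.6 uses the same definition when it summarises late toxicities separately.

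The schedule in Section 4.0 uses another clock. The row that begins "CTCAE v5.0 Solicited Late Toxicity Assessment (See section 10.0" is marked at baseline, at the post-operative assessment ("4-8 weeks Post-Surgery"), at the six-monthly visits of years 1 and 2, and at the annual visits of years 3-5. All of these except baseline are timed from surgery. The year 1-5 visits may move by 8 weeks either way. Footnote 6, attached to the post-operative column, lets that assessment take place outside its window.

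On the gap between the two clocks, Section 7.2 says: "Patients will undergo oncologic resection ideally 3-4 weeks after completion of preoperative radiation therapy per institutional standards". It continues: "If surgery is not feasible during this ideal period, it must be performed within 6 weeks", with a tolerance of 1 week. The study schema gives "3-6 weeks interval between radiation therapy and definitive surgery".

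Sections 16.3.2.7 and 16.3.2.8 analyse PROMIS-10 and TESS as change from baseline to 24 months after surgery.

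**The concern.** Objective 2.2.4 is to report long-term toxicity. If the window closes before the 24-month visit falls due, that visit contributes function and quality of life to the analysis but usually not toxicity first seen there. Slowly developing effects such as fibrosis, lost joint motion or fracture are the ones most likely to be first graded late.

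The front end has the mirror problem. The late-toxicity tables in Section 10.4 solicit localized edema, lymphedema (in most regions footnoted to the limb), tumor pain and reduced joint motion from the post-surgery assessment onward. Those findings are also common in recovery from an operation. Section 10.2.2 requires attribution only for grades 4 and 5 and treats any grade change in a listed event as treatment-related, so attribution will not separate the two. A grade 2 post-operative finding may then be late toxicity in one patient and not in another because of calendar dates alone.

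**Working it through.** The plan gives no derived figure for late toxicity, so there is none to reproduce. The check is one of timing.

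**Inputs.** Window: 3 to 24 months after radiation (16.3.2.4). Gap g from radiation to surgery: 3-4 weeks ideally, up to 6 + 1 = 7 weeks (7.2); the schema's upper limit is 6 weeks. Visits: 4-8 weeks after surgery, then 6, 12, 18 and 24 months after surgery, each ± 8 weeks (4.0). One month = 365.25/12 = 30.44 days, so 3 months = 91.3 days = 13.04 weeks.

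**Formula.** Time since radiation = g + time since surgery.

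**Back end.** A 24-month visit on its due date falls at 24 months + g, which is 7g days past the limit. It is inside only if held at least g weeks early. If visit dates are spread evenly over ± 8 weeks (assumed; the documents give no distribution), the share outside is (8 + g)/16.

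**Front end.** The post-operative visit falls g + 4 to g + 8 weeks after radiation. It enters if held at least 13.04 − g weeks after surgery. If visits are spread evenly over 4-8 weeks (also assumed), the share inside is (8 − (13.04 − g))/4, or zero if negative.

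| g (weeks) | On-time 24-month visit: days past limit | Months after radiation | Share of 24-month visits outside | Post-operative visit: weeks after radiation | Enters if held at or after (weeks post-surgery) | Share inside |
|---|---|---|---|---|---|---|
| 3 | 21 | 24.7 | 11/16 = 69% | 7-11 | 10.04 | 0 |
| 4 | 28 | 24.9 | 12/16 = 75% | 8-12 | 9.04 | 0 |
| 5 | 35 | 25.2 | 13/16 = 81% | 9-13 | 8.04 | 0 |
| 6 | 42 | 25.4 | 14/16 = 87.5% | 10-14 | 7.04 | 24% |
| 7 | 49 | 25.6 | 15/16 = 94% | 11-15 | 6.04 | 49% |

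**Calendar check.** Every radiation end date over four years was tried with every gap from 21 to 49 days. No combination puts an on-time 24-month visit inside the window. Three calendar months last 89 to 92 days, so a post-operative visit held by day 56 can first enter when surgery is on day 89 − 56 = 33. From day 92 − 56 = 36 a visit on day 56 always enters. Entry within the 4-8 week range therefore needs surgery at about 5 weeks or later.

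**Footnote 6.** If the post-operative visit runs past 8 weeks, the sixth column shows that it can also enter after earlier surgery: from about week 9 when g = 4, and from about week 10 when g = 3.

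**Middle visits.** On-time 6-, 12- and 18-month visits fall 6.7-7.6, 12.7-13.6 and 18.7-19.6 months after radiation and are always inside.

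**The case against.** The strongest reply is that the definition concerns when toxicity occurs, not when it is graded. The example adverse-event worksheet in Section 10.3.1 lists a date of occurrence. If onset decides, an on-time 24-month visit still informs most of its interval: only the last 3-7 of about 26 weeks since the 18-month visit lie outside (3/26 = 12% to 7/26 = 27%). This stands as a possible reading, but the plan does not adopt it. Solicited toxicities are graded at each evaluation, the stiffness form in Appendix IV carries only an assessment date, and nothing ties the worksheet's date to this endpoint. Fibrosis or lost motion first found on examination often has no reliable earlier onset date.

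A second reply is that a radiation anchor matches the exposure and eases comparison with other series. That is fair, and it is a reason to keep the radiation-anchored rate as a sensitivity analysis. It does not explain a window that closes just before the planned visit.

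Third, the assessments are still collected, continue annually through years 3-5, and enter the maximum-grade tables of 16.3.2.6. That is also correct: what is affected is the late-toxicity rate, not the data.

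A reader might infer that inclusion of the post-operative visit depends only on the surgery date. It does not: the visit must also fall late enough, and footnote 6 permits late visits after early surgery.

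**Conclusion.** The mismatch holds on the plan's own figures, whichever upper limit for surgery is used (6 weeks in the schema, 7 in Section 7.2). A 24-month visit on its due date is always 21-49 days outside the late-toxicity window. It counts only if held 3-7 weeks early, or if an earlier onset is documented and accepted under a rule the plan does not state. At the front end, entry of the post-operative visit turns on the combination of surgery date and visit date.

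The 69-94% should not be read as toxicity missed. It is the share of 24-month visits excluded under an assumed even spread. The rate is cumulative, so a patient already at grade 2 by the 6-, 12- or 18-month visit counts regardless. Only patients who first reach grade 2 after the 18-month visit are at stake, and the documents give no basis for estimating how many. A reader might also infer a known net bias. The back end can lower the rate and the front end can raise it, but neither effect can be sized, so the documents do not support a direction.

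This is a descriptive secondary outcome with no test or decision rule attached. The sample size of 108 and the primary analysis do not depend on it. The change is worth making because it is cheap and settles the rule before the data are seen.

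**What to change.** In 16.3.2.4, define late toxicity as any solicited toxicity of grade 2 or higher recorded after the scheduled 4-8 week post-operative assessment, up to and including the 24-month post-surgery assessment. Count that last assessment if it is held within its ± 8 week window. Include toxicity recorded between scheduled visits, so that an event that appears and resolves between two visits is not lost. State that the date of recording decides.

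Moving the anchor to surgery alone would not be enough: a permitted 24-month visit up to 8 weeks late would still fall outside a strict 24-month limit. The visit-window clause is therefore needed.

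Tabulate the post-operative assessment grades separately as early post-operative toxicity, whenever that assessment was held. Report the present definition, 3-24 months after radiation, as a sensitivity analysis for comparison with radiation-anchored series, and say there whether onset date or grading date decides. Section 16.3.2.6 takes over the new definition by its cross-reference.

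The cost is SAP wording, one extra table and one sensitivity analysis on data already planned for collection. The reported rate may shift slightly. A 24-month visit held more than 8 weeks late would still not count.

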Preexisting Condition- A preexisting condition is one that is present at the start of the study. A preexisting condition should be recorded as an adverse event if the frequency, intensity, or the character of the condition worsens during the study period. At screening, any clinically significant abnormality should be recorded as a preexisting condition. At the end of the study, any new clinically significant findings/abnormalities that meet the definition of an adverse event must also be recorded and documented as an adverse event.

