10.2.2 Assessment of Attribution

Only G4 or G5 adverse events will require an attribution. Any change in the grade of an adverse event within the list of monitored AEs will be recorded and considered to be related to treatment. Any new adverse not listed occurring within the radiated area or in close proximity will be graded and attribution defined by the study PI.

Events determined to be possibly, probably or definitely attributed to a medical treatment suggest there is evidence to indicate a causal relationship between the treatment and the adverse event.

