- 10.4 Solicited toxicities to be graded at each evaluation and pretreatment symptoms/conditions to be evaluated based on the schedule of events using the CTCAE v5.0 grading unless otherwise stated in the table below. This regimen has established safety, based on this article [https://www.thelancet.com/journals/lanonc/article/PIIS1470-2045\(22\)00638-6/fulltext](https://www.thelancet.com/journals/lanonc/article/PIIS1470-2045(22)00638-6/fulltext) so the focus is on solicited toxicities and not any adverse event after radiation therapy is completed.

ACUTE TOXICITIES – Upper Proximal Extremity			
CTCAE System/Organ/Class (SOC)	Adverse Event / Symptoms	Baseline	During RT & Preoperative Assessment

General disorders and administration site conditions	Fatigue	X	X
Skin and subcutaneous tissue disorders	Dermatitis Radiation	X	X
	Hyperpigmentation	X	X
Neoplasm benign, malignant and unspecified	Tumor pain	X	X

LATE TOXICITIES – Upper Proximal Extremity		
CTCAE System/Organ/Class (SOC)	Adverse Event / Symptoms	Post-Surgery & Follow Up
Skin and subcutaneous tissue disorders	Hyperpigmentation ¹	X
Vascular	Lymphedema ²	X
General disorders and administration site conditions	Localized edema ¹	X
Musculoskeletal and connective tissue disorders	Fibrosis deep connective tissue ¹	X
	Joint range of motion decreased ²	X
	Osteonecrosis ¹	X

Neoplasm benign, malignant and unspecified	Tumor pain ¹	X
Injury, poisoning and procedural complications	Fracture ¹	X
Gastrointestinal Disorders ¹	Esophageal fistula	X
Respiratory, thoracic and mediastinal disorders	Pneumonitis ¹	X

¹ Specific to radiation / surgery treatment area

² Specific to ipsilateral extremity / region

ACUTE TOXICITIES – Upper Distal Extremity (includes elbow)			
CTCAE System/Organ/Class (SOC)	Adverse Event / Symptoms	Baseline	During RT & Preoperative Assessment
General disorders and administration site conditions	Fatigue	X	X
Skin and subcutaneous tissue disorders	Dermatitis Radiation	X	X
	Hyperpigmentation	X	X
Neoplasm benign, malignant and unspecified	Tumor pain	X	X

LATE TOXICITIES – Upper Distal Extremity (includes elbow)		
CTCAE System/Organ/Class (SOC)	Adverse Event / Symptoms	Post-Surgery & Follow Up
Skin and subcutaneous tissue disorders	Hyperpigmentation ¹	X
Vascular	Lymphedema ²	X
General disorders and administration site conditions	Localized edema ¹	X
Musculoskeletal and connective tissue disorders	Fibrosis deep connective tissue ¹	X
	Joint range of motion decreased ²	X
	Osteonecrosis ¹	X

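### The grade 2+ late-toxicity rate in section 16.3.2.4 has no baseline condition, so symptoms present before treatment are not excluded from it

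*Combined protocol and SAP*

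**What the plan says.** Section 16.3.2.4 defines late toxicity as "toxicity occurs any time between 3 months and 24 months after completion of hypofractionated preoperative radiation therapy". The rate of grade 2 or higher "late toxicities will be estimated by the number of patients with a" toxicity of that grade in the window; this is a "late toxicity divided by the total number of evaluable patients. Exact binomial 95% confidence intervals" are planned around it. The section does not mention baseline grade, new onset or worsening.

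The provisions on collecting and recording these items are elsewhere:

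- Section 4.0 has a row "CTCAE v5.0 Solicited Late Toxicity Assessment (See section 10.0") with a mark in the baseline column as well as in the post-operative and follow-up columns.
- Section 10.4 calls for "Solicited toxicities to be graded at each evaluation and pretreatment symptoms/conditions to be evaluated based on the schedule of events". Its late tables have one time column, "Post-Surgery & Follow Up", whereas its acute tables also have a baseline column. Every late table lists tumor pain, localized edema, lymphedema and decreased joint range of motion.
- Section 10.1 says: "A preexisting condition should be recorded as an adverse event if the frequency, intensity, or the character of the condition worsens".
- Section 10.2.2 says that any "change in the grade of an adverse event within the list of monitored AEs will be recorded and considered to be related to treatment". The same section requires attribution for grade 4 and 5 events only.

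**The concern.** A soft tissue sarcoma, or an earlier non-oncologic excision (allowed by section 3.1.2), may cause pain, swelling or lost motion before radiation starts. If such a symptom is grade 2 at baseline and still grade 2 in the window, it meets the criterion in 16.3.2.4 as worded. The analyst has no general means of removing it by attribution, because grade 2 and 3 events need none.

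The baseline late-toxicity grade is scheduled, but no planned analysis uses it. By contrast, sections 16.3.2.7 and 16.3.2.8 analyze PROMIS-10 and TESS as change from baseline.

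The rate answers a named secondary objective (2.2.4). Section 16.3 also plans an exploratory comparison of secondary outcomes between proximal lower limb and other sites. If baseline symptoms differ by site, that comparison would carry the difference.

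**Working it through.** **Plan's own figures.** The documents give no expected late-toxicity rate, threshold or precision, so there is no late-toxicity figure to reproduce. The sample size in 16.2 does reproduce: [1.2816 × √(0.45 × 0.55) + 0.8416 × √(0.35 × 0.65)]² / 0.10² = 107.95, rounded up to 108, with power 80.01%. Allowing for 10% loss, 108 / 0.90 = 120. None of this depends on how late toxicity is defined.

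**What each rule would count.** Grades are for one solicited item, at baseline and in the 3-24 month window.

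| Baseline → window | 16.3.2.4 as worded | 10.1 (worsening) | 10.2.2 (any change) | Grade ≥2 and above baseline |
|---|---|---|---|---|
| 0 → 2 | counted | counted | counted | counted |
| 2 → 3 | counted | counted | counted | counted |
| 2 → 2 | counted | not counted, unless frequency or character worsens | not counted | not counted |
| 3 → 2 | counted | not counted | counted, as related | not counted |

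The rules agree on new and worsened toxicity. They disagree on persisting and improving symptoms. Two statisticians could report different rates from the same data and each cite the document.

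**Timing.** Section 7.2 puts surgery ideally 3-4 weeks after radiation, and otherwise within 6 weeks ± 1 week. The latest date is 7 weeks, before the window opens at 3 months. A baseline symptom affects the rate only if it outlasts resection.

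**Illustration of size.** Let r be the true rate of new or worsened grade 2+ toxicity, b the share of patients with a baseline grade 2+ item, and s the share of those in whom it persists. All three are assumptions, and independence is assumed. If unchanged symptoms are counted:

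reported rate = r + (1 − r) × b × s

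With r = 20% and persisting share b × s of 5%, 10% or 20%:

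- 0.20 + 0.80 × 0.05 = 24%
- 0.20 + 0.80 × 0.10 = 28%
- 0.20 + 0.80 × 0.20 = 36%

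With r = 30% and, as a further assumption, 108 patients in the denominator (exact 95% intervals):

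| b | s | Reported rate | Patients | 95% interval |
|---|---|---|---|---|
| 0 | – | 30.0% | 32/108 | 21.2-39.2% |
| 5% | 25% | 30.9% | 33/108 | 22.1-40.2% |
| 10% | 50% | 33.5% | 36/108 | 24.6-43.1% |
| 20% | 50% | 37.0% | 40/108 | 27.9-46.9% |
| 30% | 100% | 51.0% | 55/108 | 41.1-60.7% |

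Over these ranges the shift runs from about 1 to 21 points. If only worsening is counted, the result is r in every row.

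**The case against.** A reader might infer that the plan definitely counts pre-treatment symptoms and that its rate is therefore biased upward. The documents do not support that. Section 16.3.2.4 is silent on baseline, and its wording about toxicity that occurs in the window can be read as onset. Section 10.1 records a preexisting condition when it worsens, and section 10.2.2 ties recording of monitored items to a change in grade. Read together, an unchanged grade 2 need not be a late toxicity.

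The other side has further points. Tumor pain and hyperpigmentation already have a baseline entry in the acute tables, so the missing column matters mainly for edema, lymphedema, fibrosis and joint motion. The joint stiffness form in Appendix IV records attribution at every grade and is scheduled at baseline, although it is a separate scale that 16.3.2.4 does not use. Resection may resolve many tumor symptoms before the window opens. The endpoint is descriptive, and a baseline-adjusted rate could still be derived later if the scheduled baseline grades are collected.

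All of this limits the point, but the gap remains. The recording rules are not carried into the estimator. They sit uneasily with grading every solicited item at each evaluation, which puts unchanged grades in the dataset. Section 10.1 speaks of frequency, intensity or character and gives no grade comparison to program. Section 10.2.2 covers change in either direction. The choice is better fixed before the data are seen.

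**Conclusion.** Section 16.3.2.4 does not exclude symptoms present before treatment, and the rest of the document does not settle whether they count. Pre-existing grade 2 or 3 tumor pain, edema, lymphedema or reduced joint motion that persists after resection can enter the numerator, so the rate can be biased upward.

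How much is unknown, because the documents give neither the baseline prevalence of these items, nor their persistence, nor an expected late-toxicity rate. The 24-36% range is illustration and rests on the assumed 20% rate, the assumed 5-20% persisting share and independence. It falls back to 20% if only worsening is recorded.

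The effect is confined to a descriptive secondary endpoint and the exploratory site comparison of it. This is a minor point, and a cheap improvement.

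**What to change.** - In 16.3.2.4, define a late toxicity as a solicited item that is grade 2 or higher in the window and at least one grade above that item's baseline grade. State how a missing baseline grade is handled.
- Report the unadjusted rate (any grade 2 or higher in the window) beside it. The adjusted rate would miss a patient whose tumor-related edema resolves and who then develops treatment-related edema of the same grade; the pair of rates makes that trade-off visible.
- Add a baseline column to the late tables in 10.4 to match section 4.0.

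The cost is a few lines of text and a small amount of extra analysis. The headline rate may be lower than under the present wording. No visit or assessment is added, because the baseline assessment is already scheduled.
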